10.6 Retinal Fundoscopy

A retinal fundoscopy of each eye will be performed at Screening and at Day 365. Each eye will be given one of the following assignments: Normal, Abnormal-Not Clinically Significant, Abnormal-Clinically Significant. Shift tables will be provided to assess changes in retinal fundoscopy.

10.7 Infection Tests

Tests will be carried out to determine the presence of selected infections at Screening and on Day 59, Day 180 and Day 365. Infections to be tested will include Hepatitis BSAg, HCV, HTLV, CMV and VDRL. The counts and percentages of number of subjects reporting a positive infection test will be presented by visit and infection type.

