5.3 Exclusion Criteria

To participate in this study a subject may not meet any of the following criteria:

- 1. Subjects who have undergone a revascularization procedure or sympathectomy within 12 weeks prior to study entry that remains patent. A failed revascularization procedure in the previous 4 weeks is acceptable.
- 2. Subjects with grade 3 (hemorrhages, exudates) or grade 4 (papilledema) retinopathy
- 3. Subjects currently receiving immunosuppressive medications, chemotherapy, radiation therapy
- 4. Subject with aorto-iliac occlusion (greater than 75%)
- 5. Subjects that will require amputation within 4 weeks of randomization
- 6. Subjects with any co-morbid conditions likely to interfere with assessment of safety or efficacy or with an estimated life expectancy of less than 6 months
- 7. Subjects with history of drug (defined as illicit drug use) or a history of alcohol abuse (defined as regular or daily consumption of more than 4 alcoholic drinks per day) within the past 3 months

- 8. Subjects with a current history or new screening finding of malignant neoplasm except for basal cell carcinoma of the skin and squamous cell carcinoma of the skin (if excised and no evidence of recurrence)
- 9. Subjects with evidence of active infection (e.g., cellulitis, osteomyelitis) or deep ulceration exposing bone or tendon in the extremity planned for treatment
- 10. Subjects with a clinically significant abnormality in routine hematology, urinalysis, chemistry, liver function or other laboratory tests, including HIV, Hepatitis B (HepBSAg), Cytomegalovirus (CMV), Hepatitis C Virus (HCV), Venereal Disease Research Laboratory test (VDRL), prostate-specific antigen (PSA) and chorio-embryonic antigen (CEA), or signs of malignant neoplasm by radiological imaging tests, including chest radiograph at Screening or Day 1.

Specific laboratory exclusion criteria include the following:

- Hemoglobin less than 9.0 G/dl
- WBC count less than 3,000
- Platelet count less than 75,000
- Fasting glucose greater than 250 mg/dl
- AST and/or ALT greater than 3x upper limit of normal
- 11. Subjects with any other condition that in the opinion of the Investigator might put the subject at risk or interfere with his/her participation
- 12. Subjects unwilling or unable to comply with the protocol or to cooperate fully with the Investigator or site personnel

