3. STUDY OVERVIEW

This is a prospective, dose-escalation single center study to evaluate the safety and tolerability of intramuscular VM202 in subjects with critical limb ischemia.

Subjects selected for this study will have critical limb ischemia that has not responded to standard therapy with symptoms including pain at rest or ischemic ulcers.

The study will consist of four (4) cohorts with a total of 3 subjects enrolled in each cohort to VM202. The cohorts will be based on the planned different amounts of VM202 to be given. Planned levels of VM202 to be administered (defining the 4 cohorts) are the following: 2 mg, 4 mg, 8 mg and 16 mg. For each dose cohort, VM202 will be administered as a local intramuscular injection in 2 divided doses with a 2-week interval between the injections. Preliminary efficacy (hemodynamic assessments), safety and tolerability will be evaluated at Baseline (screening) and at designated time points throughout the study.

After all subjects in the first dose cohort have completed the 30-day (± 2 days) follow-up visit following the 1st dose of study drug, an interim safety evaluation will be performed with the submission of safety data to the Data Safety Monitoring Committee (DSMC). If the DSMC recommends continuing the study, the second dose cohort will be treated. This process will be repeated between the second and third dose cohort and between the third and fourth dose cohort. All 4 dose cohorts will be followed for up to five years from the time of the first dose of study drug administration. If a dose limiting toxicity (DLT) is observed in one subject in any dose group, three additional subjects will be added to the dose cohort in which the toxicity was observed. If no additional DLTs are observed in the 6 subjects in this dose level, it will be considered the maximum tolerated dose (MTD). If a DLT occurs in 2/6 subjects, then the preceding dose level will be considered the MTD.

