10.3 Clinical Laboratory Evaluation

Before the first dose of medication and at Day 15 (Pre-Dose), Day 16, Day 28, Day 59, Day 91, Day 180 and Day 365 of the study, clinical laboratory evaluations (Hematology, Chemistry, Urinalysis) will be taken. Laboratory parameters will be summarized using descriptive statistics at baseline and at each post baseline time point. Changes from baseline will also be summarized. Baseline is defined as the last non-missing value prior to first dose of study drug.

In addition, shift tables (i.e., low-normal-high at baseline versus low-normal-high at follow-up in a 3-by-3 contingency table) will be provided to assess changes in laboratory values from baseline to most abnormal follow-up result.

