|----------------|---------|-------------|----------|---------|-------------|----------|-------------------|---------|----------|-------------------|---------|----------|
| | Pos | Neg | Not Done | Pos | Neg | Not Done | Pos | Neg | Not Done | Pos | Neg | Not Done |
| Screening | n | | | n | | | n | | | n | | |
| Hepatitis BSAg | n (%) | n (%) | n (%) | n (%) | n (%) | n (%) | n (%) | n (%) | n (%) | n (%) | n (%) | n (%) |
| HCV | n (%) | n (%) | n (%) | n (%) | n (%) | n (%) | n (%) | n (%) | n (%) | n (%) | n (%) | n (%) |
| HTLV | n (%) | n (%) | n (%) | n (%) | n (%) | n (%) | n (%) | n (%) | n (%) | n (%) | n (%) | n (%) |
| CMV | n (%) | n (%) | n (%) | n (%) | n (%) | n (%) | n (%) | n (%) | n (%) | n (%) | n (%) | n (%) |
| VDRL | n (%) | n (%) | n (%) | n (%) | n (%) | n (%) | n (%) | n (%) | n (%) | n (%) | n (%) | n (%) |
| Day 59 | n | | | n | | | n | | | n | | |
| Hepatitis BSAg | n (%) | n (%) | n (%) | n (%) | n (%) | n (%) | n (%) | n (%) | n (%) | n (%) | n (%) | n (%) |
| HCV | n (%) | n (%) | n (%) | n (%) | n (%) | n (%) | n (%) | n (%) | n (%) | n (%) | n (%) | n (%) |
| HTLV | n (%) | n (%) | n (%) | n (%) | n (%) | n (%) | n (%) | n (%) | n (%) | n (%) | n (%) | n (%) |
| CMV | n (%) | n (%) | n (%) | n (%) | n (%) | n (%) | n (%) | n (%) | n (%) | n (%) | n (%) | n (%) |
| VDRL | n (%) | n (%) | n (%) | n (%) | n (%) | n (%) | n (%) | n (%) | n (%) | n (%) | n (%) | n (%) |
| Day 180 | n | | | n | | | n | | | n | | |
| Hepatitis BSAg | n (%) | n (%) | n (%) | n (%) | n (%) | n (%) | n (%) | n (%) | n (%) | n (%) | n (%) | n (%) |
| HCV | n (%) | n (%) | n (%) | n (%) | n (%) | n (%) | n (%) | n (%) | n (%) | n (%) | n (%) | n (%) |
| HTLV | n (%) | n (%) | n (%) | n (%) | n (%) | n (%) | n (%) | n (%) | n (%) | n (%) | n (%) | n (%) |
| CMV | n (%) | n (%) | n (%) | n (%) | n (%) | n (%) | n (%) | n (%) | n (%) | n (%) | n (%) | n (%) |
| VDRL | n (%) | n (%) | n (%) | n (%) | n (%) | n (%) | n (%) | n (%) | n (%) | n (%) | n (%) | n (%) |
| Day 365 | n | | | n | | | n | | | n | | |
| Hepatitis BSAg | n (%) | n (%) | n (%) | n (%) | n (%) | n (%) | n (%) | n (%) | n (%) | n (%) | n (%) | n (%) |
| HCV | n (%) | n (%) | n (%) | n (%) | n (%) | n (%) | n (%) | n (%) | n (%) | n (%) | n (%) | n (%) |
| HTLV | n (%) | n (%) | n (%) | n (%) | n (%) | n (%) | n (%) | n (%) | n (%) | n (%) | n (%) | n (%) |
| CMV | n (%) | n (%) | n (%) | n (%) | n (%) | n (%) | n (%) | n (%) | n (%) | n (%) | n (%) | n (%) |

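### Infection tests are tabulated as positives per visit and not as conversion from Screening, so new post-dose positives are not shown directly and are ambiguous in some cohorts

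*SAP*

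**What the plan says.** SAP 10.7 sets the schedule: "Tests will be carried out to determine the presence of selected infections at Screening and on Day 59, Day 180 and Day 365." It names five tests: "Infections to be tested will include Hepatitis BSAg, HCV, HTLV, CMV and VDRL." The only summary it plans is this: "The counts and percentages of number of subjects reporting a positive infection test will be presented by visit and infection type." The Table 21 layout in SAP Appendix B has, for each dose cohort, the columns "Pos | Neg | Not Done", repeated in one block per visit with the Screening block first. Nothing in it cross-classifies a post-dose result by the same subject's screening result.

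Elsewhere the SAP does relate follow-up to baseline. For laboratory values (10.3), "shift tables (i.e., low-normal-high at baseline versus low-normal-high at follow-up in a 3-by-3 contingency table) will be provided", and changes from baseline are summarised as well. Physical examination (10.4) and fundoscopy (10.6) have shift tables. Vital signs (10.5) and tumor markers (10.8) have change from baseline.

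Protocol 5.3, item 10, limits who can enter with a positive test. It excludes "Subjects with a clinically significant abnormality in routine hematology, urinalysis, chemistry, liver function or other laboratory tests", and goes on to name HIV, hepatitis B, CMV, HCV and VDRL. HTLV is not named.

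On cohort size, SAP 3 says: "The study will consist of four (4) cohorts with a total of 3 subjects enrolled in each cohort to VM202." A cohort grows to 6 if one subject has a dose-limiting toxicity. Subject-level infection results are planned as Listing 23 (SAP Appendix A).

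**The concern.** Safety is the primary objective. For infection tests, the safety question is whether a subject who was negative before VM202 became positive afterwards. Table 21 reports how many subjects are positive at each visit, which is a different quantity. A subject who enters positive and stays positive is counted again at Days 59, 180 and 365, alongside anyone newly positive.

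Such entry is possible. Exclusion item 10 turns on clinical significance and not on a positive result as such, and HTLV is tested without being named there. The Pos column in the Screening block shows that the SAP allows for it.

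Missing tests add to the difficulty. The table shows how many subjects were not tested, but not whether they were the ones positive at Screening.

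**Working it through.** The documents state no power, alpha or expected number of positives for this analysis, so there is no figure of the plan's own to reproduce. The check is what Table 21's totals can and cannot determine.

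**Inputs.** n = 3 subjects per cohort, or 6 if expanded (SAP 3); totals of positives per visit (SAP 10.7, Table 21).

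**Formula.** Take one test and compare Screening with one post-dose visit, with all n subjects tested at both. Let a be the number positive at Screening and b the number positive post-dose. The number of new positives then lies between max(0, b − a) and min(b, n − a).

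**Results over all (a, b) pairs.**

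| n | Pairs | New positive certain | None certain | Ambiguous whether any | Number of new positives exact |
|---|---|---|---|---|---|
| 3 | 16 | 6 | 7 | 3 | 12 |
| 6 | 49 | 21 | 13 | 15 | 24 |

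At n = 3 the ambiguous pairs are (1,1), (2,1) and (2,2). For (1,1), max(0, 0) = 0 and min(1, 2) = 1, so 0 or 1 new positive. The fourth inexact pair is (1,2), where a new positive is certain but may be 1 or 2. If a = 0, both bounds equal b and the number is exact. If b = 0 or a = n, there is no new positive at that visit.

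**With one missing test.** Suppose 1/3 at Screening and 1/2 later. If the untested subject was the screening positive, the two remaining subjects were both negative at Screening and the later positive is new. If the untested subject was a screening negative, the later positive can be the original one, with 0 new. So 1/3 then 1/2 also fits 0 or 1.

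**How often a cohort has mixed screening status.** The counts above are not probabilities, because the pairs are not equally likely. If screening positives simply persist and nobody converts, b = a, and at n = 3 that is ambiguous whenever 1 or 2 of the 3 are positive at Screening. If each enrolled subject is positive independently with probability p, the chance of this is 1 − (1 − p)³ − p³ = 3p(1 − p). The documents give no p. Over an assumed range:

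| Assumed p | 3p(1 − p) |
|---|---|
| 0.01 | 0.030 |
| 0.05 | 0.143 |
| 0.20 | 0.480 |
| 0.50 | 0.750 |

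**After the fix.** Cross-classifying each subject's post-dose result by screening result gives the number of new positives exactly in 16 of 16 pairs at n = 3 and 49 of 49 at n = 6.

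**Early Termination.** Protocol Table 4-1 and section 6.2.13 schedule infection tests at Early Termination. SAP 10.7 and Table 21 have no entry for that visit, whereas Table 20 (fundoscopy) combines Day 365 with Early Termination. A conversion first detected at that visit has no row in Table 21.

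**The case against.** The strongest reply is that nothing is lost. Listing 23 shows every result by subject. With 12 to 15 subjects, four scheduled visits and five tests there are 12 × 4 × 5 = 240 to 15 × 4 × 5 = 300 results, and a conversion can be found by eye. That stands, and it is the main reason the point is minor.

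Second, with complete data a hidden conversion requires a screening positive to revert to negative while another subject in the same small cohort converts. That also stands. Missing tests are the simpler route to ambiguity, and the Not Done column at least shows that they occurred.

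Third, exclusion item 10 names four of the five tabulated tests, so screening positives should be limited. This stands in part. The criterion depends on a judgement of clinical significance, and HTLV is covered only if the list is read as non-exhaustive.

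Fourth, Protocol 8.3 requires clinically significant abnormal findings after dosing to be recorded as adverse events when they meet the definition, and they would then reach the adverse event tables. This again rests on judgement and would not catch every conversion.

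Fifth, the protocol does not ask for more. Infection tests are not among the primary safety endpoints in 4.1.1, and 9.3 asks only for descriptive statistics. So this is a weaker choice of summary and not a departure from the protocol. Nor are infection tests the only repeated measure without a baseline comparison, since chest imaging is only listed. They are the exception among the repeated measures that have both a pre-dose value and a summary table.

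A reader might infer that a new infection cannot be identified from Table 21 at all, or that the table can never separate 0% from 33% conversion. The documents do not support either. The Screening block is in the same table, and with none positive at Screening every later positive is new. The 33% also divides by all 3 subjects; with one screening positive only 2 are at risk, so the contrast is 0/2 against 1/2.

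**Conclusion.** The point holds as a minor improvement. The planned summary reports positives per visit and leaves conversion to be inferred. The inference from the table fails in two situations. The first is when some but not all of a cohort are positive at Screening and the post-dose count is at least 1 but no higher than the screening count (3 of 16 pairs at n = 3, 15 of 49 at n = 6). The second is when a cohort has a screening positive and tests are missing later.

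These counts assume one post-dose visit at a time and, except for the 1/3 then 1/2 example, complete testing. How often either situation would arise cannot be said from the documents, which give neither the frequency of screening positives nor a dropout rate. No planned decision depends on this table, and Listing 23 allows any case to be resolved by subject.

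**What to change.** Keep Table 21 and supplement it with a shift from Screening. For each test and cohort, report n/N subjects negative at Screening who are positive at each post-dose visit and at any post-dose visit, counting the scheduled Early Termination test. State N at each visit as those negative at Screening and tested at that visit, and for the any-visit line as those negative at Screening with at least one post-dose test. Show subjects positive at Screening, and any not tested at Screening, on separate lines. Add one sentence to SAP 10.7 to say so.

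The cost is one table shell with its programming and validation. All the data are already collected, and no visit, test or protocol section changes.

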10.8 Tumor Marker

Measurements of selected tumor markers will be made at Screening, Day 59, Day 180 and Day 365. Tumor markers to be considered are the following: Alpha Fetoprotein (AFP), Carcino Embryonic Antigen (CEA), Prostate Specific Antigen (PSA), Cancer Antigen 19-9 (CA19-9), CA 125. Tumor marker results will be summarized using descriptive statistics at baseline and at each post baseline time point. Changes from baseline will also be summarized.

10.9 Injection Site Reaction

Assessments of the existence of an injection site reaction are planned for Day 1 (Post-Dose), Day 8, Day 15 (Post-Dose), Day 16, Day 21, Day 28 and Day 59. The number and percentage of subjects with an injection site reaction will be summarized.

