4.1.1 Primary Safety Endpoints

The primary safety endpoints include the following:

- 1. Incidence of adverse events through Day 365.
- 2. Change from Baseline in clinical chemistry, hematology, u/a at Days 15, 28, 59, 91, 180 and 365.
- 3. Injection site reactions, as measured by assessments at Days 1, 8, 15, 21, 28, and 59 using National Cancer Institute's Common Terminology for Adverse Events v3.0 criteria as follows:

Grade 1=Pain, itching, erythema;

Grade 2=Pain or swelling with inflammation or phlebitis;

Grade 3=Ulceration or necrosis that is severe or operative intervention indicated.

4. Clinically significant changes in physical examination from Baseline at Days 15, 28, 59, 91, 180 and 365.

Secondary Efficacy Endpoints

The Secondary Efficacy endpoints include the following:

- 1. Change from Baseline in hemodynamic measurements (Appendix B: ABI, TBI, and Wave Form Analysis) and TcPO₂ at Days 15, 28, 59, 91, 180 and 365.
- 2. Change from Baseline in subject-assessed pain, as measured by the VAS (Appendix C) at Days 15, 28, 59, 91, 180 and 365.
- 3. Change from Baseline in ulcer area, in square millimeters, as assessed by digital photograph and measurement of the largest contiguous ulcerated area, at Days 15, 28, 59, 91, 180 and 365.

Pharmacokinetic Evaluations

Pharmacokinetics of VM202 will be assessed using blood VM202 DNA concentration levels from samples obtained pre-dose at the first dose administration (Day 1). In addition, levels will be measured at Days 21, and 59 (if DNA is detected at Day 21).

Pharmacodynamic Evaluations

Pharmacodynamics will be assessed as the change from Day 1 in serum HGF level at Days 8, 15, 21 and 59. Potential immune response to HGF will be assessed as change

from Day 1 in level of neutralizing antibodies (anti-HGF antibodies) at Days 15, 28, 59 and 180. The ability of HGF to stimulate cell growth will be assessed as the change from Baseline in level of endothelial progenitor cell assay at Days 15, 28, 59 and 180.

Overall Study Design

The overall trial design includes: 1) a multi-dose Phase I safety and tolerability evaluation; 2) a preliminary efficacy, pharmacokinetic and pharmacodynamic evaluation; and 3) a safety review between dosing cohorts in order to meet defined safety criteria. The study will evaluate vascular assessments as primary measures of efficacy and adverse event collection and laboratory parameters as the primary monitored measures of safety (see Table 4-1).

Study Population

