7.1.6 Local Injection Site Reaction Assessment

Local injection sites reactions will be assessed using the grading defined by the National Cancer Institute's Common Terminology for Adverse Events v3.0. The grading categories are as follows and will be recorded on the CRF:

Adverse Event	Grade 1	Grade 2	Grade 3	Grade 4	Grade 5
Injection site reaction	Pain; itching; erythema	Pain or swelling, with inflammation or phlebitis	Ulceration or necrosis that is severe; operative intervention indicated		
Ulceration		Superficial ulceration <2 cm size; local wound care; medical intervention indicated	Ulceration ≥2 cm size; operative debridement, primary closure or other invasive intervention indicated (e.g. hyperbaric oxygen)	Life- threatening consequences; major invasive intervention indicated (e.g., complete resection, tissue reconstruction, flap, or grafting	Death
Allergic reaction/ hypersensitivity	Transient flushing or rash; drug fever <38°C (<100.4°F)	Rash; flushing; urticaria; dyspnea; drug fever ≥38°C (≥100.4°F	Symptomatic bronchospasm, with or without urticaria; parenteral medications(s) indicated; allergy-related edema/ angioedema; hypotension	Anaphylaxis	Death

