8.0 Adverse Events and Serious Adverse Events

8.1 Adverse Event Definition

An AE is the development of an undesirable medical condition or the deterioration of a pre-existing medical condition following or during exposure to a pharmaceutical product, whether or not considered causally related to the product. AEs will be graded according to the National Cancer Institute's Common Terminology for Adverse Events v3.0 criteria.

An undesirable medical condition can be symptoms (e.g., nausea, chest pain), signs (e.g., tachycardia, enlarged liver) or abnormal results of an investigation (e.g., laboratory findings, electrocardiogram).

Therefore, an AE would include the following:

- Any event that is new (i.e., was not seen prior to the start of the study).
- A condition detected or diagnosed after the trial medication administration, even though it may have been present prior to the start of the study.
- A pre-existing intermittent event or condition that recurs with increased intensity and/or frequency after the start of the study.
- A pre- or post-treatment event that results from study participation (i.e., invasive procedures, modification of subject's therapeutic regimen)
- A change in blood pressure or heart rate that results in discontinuation of dosage or that exceeds protocol-specified criteria

An AE does not include the following:

- The disease or disorder being studied, or a sign or symptom of that disease or disorder, unless it is more severe than expected for the subject's condition.
- An overdose of the study medication if the subject is asymptomatic.
- A medical or surgical procedure (e.g., surgery, endoscopy, tooth extraction).
 Depending on the trial design, such a procedure may be the result of an AE or may result in an AE, but is not an AE itself.
- A pre-existing condition or disease that does not worsen following study drug administration.
- Hospitalization for elective surgery for a pre-existing disease or condition that did not worsen or for cosmetic surgery.

In this study an AE can include an undesirable medical condition occurring at any time after screening procedures have been started until the final follow-up visit, even if no study treatment has been administered.

When an adverse event occurs, the Investigator must:

- 1. assess whether or not the test article caused the AE;
- 2. determine the intensity of the AE;
- 3. record the action taken regarding the test article;

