- 4. indicate whether the AE led to discontinuation of the subject from the study; and
- 5. determine if the AE is serious.

All AEs that occur in any subject enrolled, before treatment, during treatment, or up to and including study Day 365 whether or not related to the study drug, must be recorded on the appropriate CRF form provided.

The following are definitions of levels of severity:

- Mild: an awareness of symptoms but easily tolerated
- Moderate: symptoms interfering with daily activities
- Severe: incapacitating, with inability to perform normal daily activities.

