8.5 Documentation of AEs and SAEs

All AEs occurring during the study must be recorded in the subject's medical records and on the AE page of the CRF, even if the AE is considered by the Investigator to be unrelated to the use of the study drug. SAEs that occur during the study must be documented in the subject's medical record, on the AE page of the CRF, and on the SAE Report Form.

A separate SAE CRF will be used for all SAEs. For SAEs which are related and within a specific time period, a single form can be used. An assessment of the relationship of each event to the study therapy will be added for each SAE on the form. Following initial reporting of the event, the Investigator will make every effort to establish a diagnosis of the event based on the presenting signs, symptoms, and/or other clinical information. In such cases, the diagnosis will be documented as the AE and/or SAE and not the individual signs/symptoms.

Death will not be reported as a serious adverse event. Death will be reported as the outcome of the event. When a subject expires, please use the cause of Death (acute MI, CVA, sepsis) as the SAE and the outcome as Death. When no cause of Death is apparent, please use cardio-pulmonary arrest as the SAE.

If a clinically significant, abnormal laboratory finding or other abnormal assessment meets the definition of an AE or SAE, then the AE page of the CRF and the SAE Report Form must be completed, as appropriate. A diagnosis, if known, or clinical signs and symptoms if the diagnosis is unknown, rather than the clinically significant abnormal laboratory finding, will be recorded on the AE page of the CRF and on the SAE Report Form, as appropriate. If no diagnosis is known and clinical signs and symptoms are not present, then the abnormal finding will be recorded. If an isolated laboratory abnormality is an SAE, then the following will be performed: 1) the laboratory data will be recorded in the SAE Report Form with the reference range and all preceding measurement(s) value(s), including Baseline value(s), and 2) copies of the laboratory reports and reference ranges will be sent with the SAE Report Form.

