| Subject reported an Injection Site I | Reaction? | | | |
| Yes | n (%) | n (%) | n (%) | n (%) |
| No | n (%) | n (%) | n (%) | n (%) |

path\t_program.sas date time

Programmer Note:

Viromed Co., Ltd. Protocol Number: US-06-1-001

Table 24 Concomitant Medications [1] Safety Population

| ATC Drug Class / Medication Term | VM202- 2 mg | VM202- 4 mg | VM202- 8 mg | VM202- 16 mg |
|--|-------------|-------------|-------------|--------------|
| | (N=) | (N=) | (N=) | (N=) |
| Subjects Receiving any Concomitant Medications | n (%) | n (%) | n (%) | n (%) |
| Drug Class 1 Medication Term 1 Medication Term 2 | n (%) | n (%) | n (%) | n (%) |
| | n (%) | n (%) | n (%) | n (%) |
| | n (%) | n (%) | n (%) | n (%) |
| Drug Class 2 | n (%) | n (%) | n (%) | n (%) |
| Medication Term 1 | n (%) | n (%) | n (%) | n (%) |
| Medication Term 2 | n (%) | n (%) | n (%) | n (%) |

[1] At each level of summation (overall, ATC drug class, medication term), subjects reporting more than medication are counted only once.

path\t_program.sas date time

Viromed Co., Ltd. Protocol Number: US-06-1-001

Table 25 VM202 DNA Levels (unit) ITT Population

| | VM202- 2 mg (N=) | | VM202-4 mg (N=) | | VM202-8 mg (N=) | | VM202-16 | i mg (N=) |
|--------------|-------------------|--------------|------------------|--------------|------------------|--------------|--------------|--------------|
| | Result | Change [2] | Result | Change [2] | Result | Change [2] | Result | Change [2] |
| Baseline [1] | | | | | | | | |
| N | n | | n | | n | | n | |
| Mean (SD) | xx.x (xx.xx) | | xx.x (xx.xx) | | xx.x (xx.xx) | | xx.x (xx.xx) | |
| Median | XX.X | | XX.X | | XX.X | | XX.X | |
| Min, Max | XX, XX | | XX, XX | | XX, XX | | XX, XX | |
| Day 21 | | | | | | | | |
| N | n | n | n | n | n | n | n | n |
| Mean (SD) | xx.x (xx.xx) | xx.x (xx.xx) | xx.x (xx.xx) | xx.x (xx.xx) | xx.x (xx.xx) | xx.x (xx.xx) | xx.x (xx.xx) | xx.x (xx.xx) |
| Median | XX.X | XX.X | XX.X | XX.X | XX.X | XX.X | XX.X | XX.X |
| Min, Max | XX, XX | XX, XX | XX, XX | XX, XX | XX, XX | XX, XX | XX, XX | XX, XX |
| Day 59 | | | | | | | | |
| N | n | n | n | n | n | n | n | n |
| Mean (SD) | xx.x (xx.xx) | xx.x (xx.xx) | xx.x (xx.xx) | xx.x (xx.xx) | xx.x (xx.xx) | xx.x (xx.xx) | xx.x (xx.xx) | xx.x (xx.xx) |
| Median | XX.X | XX.X | XX.X | XX.X | XX.X | XX.X | XX.X | XX.X |
| Min, Max | xx, xx | xx, xx | xx, xx | xx, xx | xx, xx | xx, xx | xx, xx | xx, xx |

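### The SAP reports the graded injection-site endpoint as one ungraded Yes/No per subject, and its laboratory shift tables drop the Low of any subject who also has a High

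*SAP*

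**What the plan says.** **Injection site.** Protocol 4.1.1 gives the third primary safety endpoint as "Injection site reactions, as measured by assessments at Days 1, 8, 15, 21, 28, and 59", graded by CTCAE v3.0, with Grades 1, 2 and 3 written out. Protocol 7.1.6 repeats the scale and adds: "The grading categories are as follows and will be recorded on the CRF". SAP 10.9 lists seven assessments (the protocol's six days plus Day 16), speaks only of whether a reaction exists, and then states: "The number and percentage of subjects with an injection site reaction will be summarized". The Table 23 shell in SAP Appendix B asks a single question, beginning "Subject reported an Injection Site", answered Yes or No by cohort. It has no grade row and no visit row, and its programmer note is blank.

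**Laboratory.** The second primary safety endpoint is "Change from Baseline in clinical chemistry, hematology, u/a at Days 15, 28, 59, 91, 180 and 365". Tables 16.1 to 16.3 plan results and changes from baseline by visit. For categorical abnormalities, Protocol 9.3 calls for a summary in both directions, low and high. SAP 10.3 plans three-by-three shift tables from baseline to the worst follow-up value. The programmer notes to Tables 17.1, 17.2 and 17.3 then say that a subject with both a High and a Low after dosing is counted as High.

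**The concern.** Safety and tolerability are the primary objective, and the study escalates the dose of a locally injected product across four cohorts. A reader of the study report will want to know whether local reactions become worse as the dose rises, and when they occur. Table 23 can show neither, although the endpoint is defined by grade and day and both are collected.

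In the laboratory tables, a reader who counts subjects with a low value of an analyte will use the shift tables, because no other planned table classifies results as low, normal or high. The High rule can make that count too small, always in the same direction.

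**Working it through.** There is no stated power, alpha or event figure to reproduce: Protocol 9.1 bases the sample size on feasibility. The check compares what is collected with what is tabulated.

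**1. Injection-site information in and out.**
- Assessments per subject: 7 in SAP 10.9 (Days 1, 8, 15, 16, 21, 28, 59), 6 in the endpoint (no Day 16). Each has four outcomes: none, Grade 1, 2 or 3.
- Planned size: 12 to 15 subjects. For 12: 12 × 7 = 84 assessments (12 × 6 = 72 on the endpoint's days) become 12 Yes/No values. For 15: 15 × 7 = 105 (15 × 6 = 90) become 15.
- Table 23 has 2 rows × 4 cohorts = 8 cells. A worst-grade table has 4 rows × 4 cohorts = 16.

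**2. What Table 23 cannot separate.** Take two cohorts of three. In A, each subject has one Grade 1 reaction at one visit. In B, each has Grade 3 at all seven assessments.
- Table 23: A is Yes 3 (100%); B is Yes 3 (100%).
- Worst grade as none/1/2/3: A is 0/3/0/0; B is 0/0/0/3.

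**3. Laboratory shift rule.** It acts within one analyte and on post-dose results only. A subject with only Low results is still counted as Low, and a Low at baseline keeps its column. When both directions occur after dosing, the Low is never counted.
- Against Protocol 9.3 (both directions), each such subject lowers the Low count by one: 1/3 = 33.3 percentage points in a cohort of 3, or 1/6 = 16.7 in an expanded cohort of 6. The shells state no denominator, so cohort size is an assumption.
- Against SAP 10.3 (worst value), the rule changes the result only when the Low is the more extreme. If that holds for a share s of such subjects (assumed, 0 to 1), the mean loss per case is s × 33.3 = 0 to 33.3 points at n = 3, or s × 16.7 = 0 to 16.7 at n = 6.

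**4. How often this could happen.** The documents give no frequency, so this is illustration only. Assume that each of the 7 post-baseline visits in SAP 10.3 gives a High with probability p and a Low with probability p, independently across visits. Then P(any Low) = 1 − (1 − p)^7 and P(both) = 1 − 2(1 − p)^7 + (1 − 2p)^7. The masked share of subjects with any Low is the ratio of the second to the first.
- p = 1%: P(both) 0.4%, P(any Low) 6.8%, masked share 5.9%
- p = 2.5%: 2.3%, 16.2%, 14.3%
- p = 5%: 8.2%, 30.2%, 27.1%
- p = 10%: 25.3%, 52.2%, 48.5%

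A subject whose values stay abnormal in one direction would have both less often than independence implies.

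**5. Analyte list.** Protocol Table 7-1 has 12 chemistry + 6 liver tests = 18. The Table 17.2 note names 17; the missing one is potassium.

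**The case against.** **Other output covers grade.** A new reaction is an adverse event under Protocol 8.1, and Protocol 8.5 requires every adverse event to be recorded in the medical record "and on the AE page of the CRF, even if the AE is considered by the Investigator to be unrelated". It would then reach Table 13, which shows highest severity by cohort. A reader might infer that Table 13's scale is ambiguous, because Protocol 8.1 also gives a functional scale ("Mild: an awareness of symptoms but easily tolerated"). The shell does not support that inference. The functional scale has three levels, whereas Table 13 has five columns, the last two being life-threatening and death. Those match CTCAE Grades 4 and 5 as laid out in Protocol 7.1.6, and Protocol 8.1 names CTCAE for grading adverse events. So Table 13 is a real partial substitute. It still has no visit dimension, and the SAP does not designate it to report endpoint 3.

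**No data are lost.** This stands. SAP 4 promises individual CRF data in listings, Listing 8 covers injection-site reactions, and Listings 17 to 19 and the minima in Tables 16.1 to 16.3 keep the laboratory values. A listing is not a summary, however, and the minima do not count subjects.

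**Three Grade 3 reactions would surface elsewhere.** Probably. Injection-site necrosis within two weeks is a DLT under Protocol 7.1.9, and some such events may be serious and appear in Table 15. But severe ulceration without necrosis is not a listed DLT, and the SAP's list of tables has no summary of DLTs by cohort.

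**A by-visit table is nearly a listing.** At the endpoint's six visits it needs 6 × 4 × 4 = 96 cells for 72 assessments in 12 subjects. This is fair as to bulk. The overall worst-grade block is the essential part; the visit block follows from the endpoint naming its days.

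**The High rule only operationalizes the SAP.** Neither document gives a metric for comparing a High with a Low, and the shells do have both rows. It is true that the departure from SAP 10.3 is conditional on the Low being more extreme. The undercount against Protocol 9.3 is not conditional once a subject has both.

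**Low is not shown to be the direction that matters.** A reader might infer that it is from the lower entry limits for hemoglobin, white cells and platelets in Protocol 5.3. The same list sets upper limits for glucose and AST/ALT, so the inference fails.

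**Conclusion.** Two planned summaries fall short of what the protocol defines.

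- **Injection site.** Table 23 omits grade and day from an endpoint defined by both. In a cohort of three, the mildest and the worst graded outcomes print the same 100%. This follows directly from the text.
- **Laboratory shifts.** The High rule removes the Low of every subject with both directions from the only planned low/high laboratory summary. The size is one subject per case: 33 points of three or 17 of six if cohort size is the denominator. The number of cases is unknown.

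A reader might go further and infer that local severity goes unreported, that the laboratory endpoint is not analysed, or that dose escalation is compromised. The documents do not support these readings. Table 13 and the listings carry severity, Tables 16.1 to 16.3 cover change from baseline as worded, and under Protocol 9.4 the DSMC reviews all safety data, including severity, rather than these tables. The effect is on the study report.

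Two further items are clerical only. Potassium is absent from the named analytes, but the Table 16.2 note also calls for all available analytes, the Table 17.2 list is introduced as inclusive, and Listing 18 covers chemistry. The Day 1 block of Table 11 offers a DLT from an earlier injection as a reason for not dosing, which cannot apply before the first injection.

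**What to change.** - **SAP 10.9 and Table 23:** report the number of subjects by worst CTCAE grade (none, 1, 2, 3) per cohort, overall and at each of the endpoint's visits. State how Day 16 is treated: it is in Protocol Table 4-1 and SAP 10.9 but not in the endpoint's list of days.
- **Tables 17.1 to 17.3:** delete the High rule and give two shifts per analyte, baseline to lowest and baseline to highest post-dose value. No tie rule is then needed. Align the wording of SAP 10.3, and state the denominator.
- **Clerical:** name potassium in the notes to Tables 16.2 and 17.2, and correct the Day 1 row in Table 11.

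The cost is a few shell edits and slightly more programming: Table 23 grows from 8 cells to 16 overall plus 96 by visit, and each analyte has two shift blocks instead of one. No new data are needed.
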